10.5.4 Follow-up

10.5.4.1 Potential Hy's Law Criteria Are Not Met

If the subject does not meet potential Hy's Law criteria the investigator will:

- Inform the study representative that the subject has not met potential Hy's Law criteria
- Perform follow-up on subsequent laboratory results according to the guidance provided in the Clinical Study Protocol.

10.5.4.2 Potential Hy's Law Criteria Are Met

If the subject does meet potential Hy's Law criteria the investigator will:

- Determine whether potential Hy's Law criteria were met at any study visit prior to starting study treatment
- Notify the sponsor study representative who will then inform the study team.
- Within 1 day of potential Hy's Law criteria being met, the investigator will report the case as an SAE of Potential Hy's Law; serious criteria 'Important medical event' and causality assessment 'yes/related' according to clinical study protocol process for SAE reporting

The medical monitor contacts the investigator, to provide guidance, discuss and agree on an approach for the study subjects' follow-up (including any further laboratory testing) and the continuous review of data.

Subsequent to this contact the investigator will:

- Monitor the subject until liver biochemistry parameters and appropriate clinical symptoms and signs return to normal or baseline levels, or as long as medically indicated. Complete follow-up SAE form as required.
- Investigate the etiology of the event and perform diagnostic investigations as discussed with the medical monitor
- Complete the relevant eCRF Modules as information becomes available

10.5.5 Review and Assessment of Potential Hy's Law Cases

The instructions in this section should be followed for all cases where potential Hy's Law criteria are met.

As soon as possible after the biochemistry abnormality was initially detected, the medical monitor will contact the investigator in order to review available data and agree on whether there is an alternative explanation for meeting potential Hy's Law criteria other than DILI caused by the investigational product, to ensure timely analysis and reporting to health authorities per local requirements from the date potential Hy's Law criteria were met. The medical monitor and Global Safety Physician will also be involved in this review together with other subject matter experts as appropriate.

According to the outcome of the review and assessment, the investigator will follow the instructions below.

Where there is an agreed alternative explanation for the ALT or AST and TBL elevations, a determination of whether the alternative explanation is an AE will be made and subsequently whether the AE meets the criteria for a SAE:

- If the alternative explanation is **not** an AE, record the alternative explanation on the appropriate CRF
- If the alternative explanation is an AE/SAE, update the previously submitted potential Hy's Law SAE and AE CRFs accordingly with the new information (reassessing event term; causality and seriousness criteria) following sponsor's standard processes

If it is agreed that there is **no** explanation that would explain the ALT or AST and TBL elevations other than the investigational product:

- Send the updated SAE (report term ‘Hy’s Law’) according to the sponsor’s standard processes.
- The ‘Medically Important’ serious criterion should be used if no other serious criteria apply
- As there is no alternative explanation for the Hy’s Law case, a causality assessment of ‘related’ should be assigned

If, there is an unavoidable delay of over 15 calendar days in obtaining the information necessary to assess whether or not the case meets the criteria for Hy’s Law, then it is assumed that there is no alternative explanation until such time as an informed decision can be made:

- Provide any further update to the previously submitted SAE of Potential Hy’s Law (report term now ‘Hy’s Law case’), ensuring causality assessment are related to the investigational product and seriousness criteria is medically important, according to the clinical study protocol process for SAE reporting
- Continue follow-up and review according to agreed plan. Once the necessary supplementary information is obtained, repeat the review and assessment to determine whether Hy’s Law criteria are still met. Update the previously submitted potential Hy’s Law SAE report following clinical study protocol process for SAE reporting, according to the outcome of the review and amend the reported term if an alternative explanation for the liver biochemistry elevations is determined

10.5.6 Laboratory Tests

The list below represents the standard, comprehensive list of follow-up tests which are recommended but not mandatory when using a central laboratory. For studies using a local laboratory, the list may be modified based on clinical judgement. If required, for additional assistance on which tests could be used to evaluate other potential causes of liver dysfunction, consult with the Hepatic Safety Knowledge Group. Any test results need to be recorded.

Hy's Law lab kit for central laboratories

Additional standard chemistry and coagulation tests	GGT LDH Prothrombin time INR
Viral hepatitis	IgM anti-HAV IgM and IgG anti-HBc HBsAg HBV DNA IgM and IgG anti-HCV HCV RNA IgM anti-HEV HEV RNA
Other viral infections	IgM & IgG anti-CMV IgM & IgG anti-HSV IgM & IgG anti-EBV
Alcoholic hepatitis	Carbohydrate deficient transferrin (CD-transferrin)
Autoimmune hepatitis	Antinuclear antibody (ANA) Anti-Liver/Kidney Microsomal Ab (Anti-LKM) Anti-Smooth Muscle Ab (ASMA)
Metabolic diseases	alpha-1-antitrypsin Ceruloplasmin Iron Ferritin Transferrin Transferrin saturation

10.6 Appendix 6 - Genetic Research

Rationale and Objectives

MedImmune intends to collect and store DNA for genetic research to explore how genetic variations may affect clinical parameters, risk and prognosis of diseases, and the response to medications. Genetic research may lead to better understanding of diseases, better diagnosis of diseases or other improvements in health care and to the discovery of new diagnostics, treatments or medications. Genetic research samples may be used to perform whole genome and whole exome sequencing.

In addition, collection of DNA samples from populations with well described clinical characteristics may lead to improvements in the design and interpretation of clinical trials and, possibly, to genetically guided treatment strategies.

Genetic Research Plan and Procedures

Selection of genetic research population and study selection record

All subjects will be asked to participate in this genetic research. Participation is voluntary and if a subject declines to participate there will be no penalty or loss of benefit. The subject will not be excluded from any aspect of the main study.

Inclusion Criteria

For inclusion in this genetic research, subjects must fulfill all of the inclusion criteria described in the main body of the Clinical Study Protocol **and** provide informed consent for the genetic sampling and analyses.

Exclusion Criteria

Exclusion from this genetic research may be for any of the exclusion criteria specified in the main study or any of the following:

- Previous allogeneic bone marrow transplant
- Non-leukocyte depleted whole blood transfusion in 120 days of genetic sample collection

Discontinuation of Subjects from this Genetic Research

Specific reasons for discontinuing a subject from this genetic research are:

Withdrawal of consent for genetic research: Subjects may withdraw from this genetic research at any time, independent of any decision concerning participation in other aspects of the main study. Voluntary discontinuation will not prejudice further treatment. Procedures for discontinuation are outlined in Section [4.1.6](#) of the main Protocol.

Collection of Samples for Genetic Research

The blood sample for genetic research will be obtained from the subjects at Visit 2 provided that the subject has given explicit consent for this. Although DNA variants are a stable parameter, early sample collection is preferred to avoid introducing bias through excluding subjects who may withdraw due to an AE, such subjects would be important to include in any genetic analysis. If for any reason the sample is not collected at Visit 2, it may be taken at any visit until the last study visit. Only one sample should be collected per subject for genetic research during the study. Samples will be collected, labelled, stored and shipped as detailed in the Laboratory Manual.

Coding and Storage of DNA Samples

The processes adopted for the coding and storage of samples for genetic analysis are important to maintain subject confidentiality. Samples will be stored for a maximum of *15 years*, from the date of last subject last visit, after which they will be destroyed. DNA is a finite resource that is used up during analyses. Samples will be stored and used until no further analyses are possible or the maximum storage time has been reached.

An additional second code will be assigned to the blood either before or at the time of DNA extraction replacing the information on the sample tube. Thereafter, the sample will be identifiable by the second, unique number only. This number is used to identify the sample and corresponding data at the MedImmune genetics laboratories, or at the designated organisation. No personal details identifying the individual will be available to any person (MedImmune employee or designated organisations working with the DNA).

The link between the subject randomisation code and the second number will be maintained and stored in a secure environment, with restricted access at MedImmune or designated organisations. The link will be used to identify the relevant DNA samples for analysis, facilitate correlation of genotypic results with clinical data, allow regulatory audit, and trace samples for destruction in the case of withdrawal of consent.

Ethical and Regulatory Requirements

The principles for ethical and regulatory requirements for the study, including this genetics research component, are outlined in Section [7.2](#) of the main Protocol.

Informed Consent

The genetic component of this study is optional and the subject may participate in other components of the main study without participating in the genetic component. To participate in the genetic component of the study the subject must sign and date both the consent form for the main study and the genetic component of the study. Copies of both signed and dated consent forms must be given to the subject and the original filed at the study centre. The principal investigator(s) is responsible for ensuring that consent is given freely and that the

subject understands that they may freely discontinue from the genetic aspect of the study at any time.

Subject Data Protection

MedImmune will not provide individual genotype results to subjects, any insurance company, any employer, their family members, or general physician unless required to do so by law.

Extra precautions are taken to preserve confidentiality and prevent genetic data being linked to the identity of the subject. In exceptional circumstances, however, certain individuals might see both the genetic data and the personal identifiers of a subject. For example, in the case of a medical emergency, a MedImmune physician or an investigator might know a subject's identity and also have access to his or her genetic data. Also Regulatory authorities may require access to the relevant files, though the subject's medical information and the genetic files would remain physically separate.

Data Management

Any genotype data generated in this study will be stored at a secure system at MedImmune and/or designated organisations to analyse the samples.

The results from this genetic research may be reported in a separate report from the CSR or published in scientific journals.

MedImmune and its designated organisations may share summary results (such as genetic differences from groups of individuals with a disease) from this genetic research with other researchers, such as Hospitals, Academic Organisations, or Health Insurance Companies. This can be done by placing the results in scientific databases, where they can be combined with the results of similar studies to learn even more about health and disease. The researchers can only use this information for health-related research purposes. Researchers may see summary results but they will not be able to see individual subject data or any personal identifiers.

Some or all of the clinical datasets from the main study may be merged with the genetic data in a suitable secure environment separate from the clinical database.

Statistical Methods and Determination of Sample Size

The number of subjects that will agree to participate in the genetic research is unknown. It is therefore not possible to establish whether sufficient data will be collected to allow a formal statistical evaluation or whether only descriptive statistics will be generated. A Statistical Analysis Plan will be prepared where appropriate.

10.7 Appendix 7 - Biological Samples

Storage, Re-use and Destruction of Biological Samples

Biological samples will be stored for a maximum of 15 years from the date of the Last Subject's Last Visit, after which they will be destroyed.

The results of biomarker and microbiome research will be reported either in the CSR itself or as an addendum, or separately in a scientific report or publication. The results of this research may be pooled with biomarker data from other studies with the study drug to generate hypotheses to be tested in future research. ADA samples will be stored for up to 2 years after marketing approval.

Labelling and Shipment of Biological Samples

The principal investigator ensures that samples are labelled and shipped in accordance with the Laboratory Manual and the Biological Substance, Category B Regulations (materials containing or suspected to contain infectious substances that do not meet Category A criteria).

Any samples identified as Infectious Category A materials are not shipped and no further samples will be taken from the subject unless agreed with MedImmune and appropriate labelling, shipment and containment provisions are approved.

Chain of Custody of Biological Samples

A full chain of custody is maintained for all samples throughout their lifecycle.

The principal investigator at each study site keeps full traceability of collected biological samples from the subjects while in storage at the study site until shipment or disposal (where appropriate) and keeps documentation of receipt of arrival. The sample receiver keeps full traceability of the samples while in storage and during use until used or disposed of or until further shipment and keeps documentation of receipt of arrival.

MedImmune keeps oversight of the entire life cycle through internal procedures, monitoring of study sites and auditing of external laboratory providers.

Stool samples retained for further use are registered in the Translational Sciences Biorepository during the entire life cycle. Blood samples for future genetic and non-genetic testing along with any surplus PK or ADA samples will go to the AstraZeneca Biobank in Gothenburg.

10.8

C _{trough}	Trough plasma concentration, measured at the end of a dosing interval, taken directly before next administration
eCRF	Electronic Case Report Form
eGFR	Estimated glomerular filtration rate
ECG	Electrocardiogram
GLP-1	glucagon-like peptide-1
² H	deuterium
HbA1c	Glycated hemoglobin
IM	Immunogenicity
ITT	Intent-to-treat
IV	intravenous
IWRS	Interactive web response system
MedDRA	Medical dictionary for regulatory activities
MMTT	Mixed-meal tolerance test
MRI	Magnetic resonance imaging
MRS	Magnetic resonance spectroscopy
P	Probability
PD	Pharmacodynamic(s)
PK	Pharmacokinetic(s)
PR	ECG PR interval
PT	MedDRA preferred term
QRS	ECG QRS interval
QT	ECG QT interval
QTcF	ECG QT interval corrected for heart rate using Fridericia's formula
RR	ECG RR interval
SAE	Serious adverse event
SAP	Statistical analysis plan
SPP	Statistical Programming Plan

Abbreviation or Specialized Term	Definition
SC	Subcutaneous
SID	Subject ID
SOC	MedDRA system organ class
T	Time
T2DM	Type 2 Diabetes Mellitus
ULN	upper limit of normal
WHO-DD	WHO Drug Dictionary enhanced

1 INTRODUCTION

This document describes the statistical analysis methodology for protocol D5670C00022 (Amendment 6, 15Jul2020), a Phase 2 study to evaluate the effect of MEDI0382 on hepatic glycogen levels post prandially versus placebo in Part A and to compare the effect of MEDI0382 on hepatic glycogen levels versus placebo and liraglutide in Part B in overweight or obese subjects with T2DM. This document details the statistical summaries relating to each study objective and describes the general conventions and definitions that will be used. In addition, a set of table templates and specifications will be included in a statistical programming plan (SPP) to complement this document.

2 STUDY OVERVIEW

2.1 Study Objectives

2.1.1 Primary Study Objective(s)

- To assess the effect of MEDI0382 on hepatic glycogen levels post prandially versus placebo after 28 days (Part A) and 35 days (Part B) of treatment

2.1.2 Secondary Study Objectives

- To assess the effect of MEDI0382 on hepatic glycogen levels post prandially versus liraglutide after 35 days of treatment (Part B only)
- To assess the effect of MEDI0382 on hepatic fat fraction versus placebo after 35 days of treatment (Part B only)
- To evaluate the safety and tolerability of MEDI0382 [REDACTED]
- To characterize the immunogenicity profile of MEDI0382 [REDACTED]
[REDACTED]

2.1.3 Exploratory Study Objectives

- [REDACTED]
- [REDACTED]
- [REDACTED]

Figure 1 consists of six horizontal bars. The first five bars are black with a white rectangular center, representing a baseline or control condition. The last bar is black with a white 'S' at its right end, representing a stimulus condition.

2.2 Study Design

This exploratory Phase 2 study has 2 parts (Part A and Part B).

Part A is a randomized, double-blind, placebo-controlled sub-study to evaluate the effect of MEDI0382 ([REDACTED] administered once daily SC for 28 days on hepatic glycogen metabolism in overweight or obese subjects with T2DM. Part A is planned to randomize up to 20 subjects. Subjects will be consented, screened for suitability, and randomized within 60 days if eligible. Subjects from Part A will not be re-enrolled in Part B.

Part B is contingent on the results from Part A such that the combined sample size of two parts will ensure at least 80% power to detect the treatment effect observed from Part A using the standard deviation information also observed from Part A. If the minimal required sample size for Part B is less than or equal to 10 subjects per arm, Part B will be conducted.

Part B is an exploratory Phase 2 randomized, double-blind, placebo-controlled and open label active comparator sub-study to evaluate the effect of MEDI0382 on hepatic glycogen metabolism in overweight and obese subjects with T2DM subjects with the exact sample size determined by the results from Part A. Subjects in Part B will be randomized to receive double-blind MEDI0382 ([REDACTED]) or placebo or open label liraglutide (titrated from 0.6 to 1.8 mg) once daily SC for 35 days.

Part A:

The study will involve measurement of hepatic glycogen content using a carbon (C)-13 MRS based technique before and after 28 days of treatment. Subjects will undergo a 5-day washout

period where metformin therapy will be suspended at the beginning of the study starting from Day -4 (metformin dosing to resume on Day 2) and the end of the study starting from Day 25 (metformin dosing to resume on Day 30). Across the course of the study (up to 126 days in total including screening) subjects will have a total of 6 study visits, 6 nights of inpatient stay and will undergo a total of 10 MRS scans alongside additional assessments and blood sampling.

Part B:

In Part B a comparison will be made between MEDI0382, [REDACTED] [REDACTED] placebo and liraglutide once daily titrated from 0.6 to 1.8 mg in 7-day intervals. The treatment duration will be 35 days in each treatment group, with subjects randomized to liraglutide spending 21 days at 1.8 mg, in contrast subjects randomized to MEDI0382 will spend 14 days at top dose of 300 µg.

The procedures for subjects who go through to the completion of the visit on Day 8, are identical to Part A; aside from the MRS scanning and related activities that will occur at baseline prior to treatment, then at T = 0, 5, 14 and 24 hours and at the end of the 35 day treatment period as detailed in the schedule of events. The duration of MRS scans will be approximately 40 minutes with the exception of the baseline and end of treatment scans used for liver fat evaluation which will be prolonged and up to 1 hour 45 minutes in duration.

2.3 Treatment Assignment and Blinding

An IWRS will be used for randomization to a treatment group and assignment of investigational product kit numbers. A subject is considered randomized into the study when the IWRS provides the assignment of the subject's investigational product kit number.

Eligible subjects will be randomized at a 1:1 ratio following screening to receive either blinded MEDI0382 SC or placebo SC (Part A) or randomized at a 1:1:1 ratio following screening to receive either blinded MEDI0382 SC or placebo SC or open-label liraglutide SC (Part B). The IWRS will assign a unique randomization code and treatment group to the subject at the time of randomization. Subjects who withdraw from the study may be replaced, if deemed necessary by the medical monitor, to ensure that safety data are collected on a sufficient number of subjects.

In Part A only, this is a double-blind study in which MEDI0382 and placebo [REDACTED] [REDACTED] Neither the subject nor any of the investigator or sponsor staff who are involved in the treatment or clinical evaluation of subjects will be aware of treatment received.

[REDACTED] To maintain the blind in Part A of the study, investigational product (MEDI0382 and placebo) prefilled syringes will be handled by an unblinded investigational product manager or unblinded study personnel who will not be involved in the treatment or clinical evaluation of subjects. An unblinded site monitor will perform investigational product accountability, and this will be a different person from the blinded site monitor who will oversee other aspects of the study at the clinical site.

[REDACTED]. Each subject will know the volume of investigational product they have been instructed to select and administer, the subject and site staff are blinded with respect to whether they are receiving MEDI0382 or placebo. Liraglutide used in Part B will be open-label.

The site will maintain a written plan detailing which staff members are blinded/unblinded and the process of investigational product administration used to maintain the blind.

2.4 Sample Size

CCI

3 STATISTICAL METHODS

3.1 General Considerations

In the event that there is a delay in data delivery or the full set of results is not expected to be available in timely manner (for example; follow-up of positive ADA results at 3 and 6

months after the follow-up visit) an initial database lock in Part B for the purpose of clinical study analysis and reporting will be performed when the last randomized subject completes the final visit or is discontinued prior to that visit. Final database lock will occur once all results have been received in the database.

In the event that an initial DBL is required, results received after this point may be reported in the clinical study report addendum.

Data will be presented in data listings sorted by study part, treatment, subject number and date collected, where appropriate. Tabular summaries will be presented by study part and treatment. Categorical data will be summarized by study part and treatment with the number and percentage of subjects within each category. In general, continuous variables will be summarized by study part and treatment with descriptive statistics including mean, standard deviation, median, minimum, and maximum. For some variables, the geometric mean and 95% CI may be presented.

All available data will be included in the analyses and missing data will not be imputed except as specified in the calculation of the AUC values. Unless specified otherwise, baseline values will be defined as the last valid assessment prior to the first administration of study medication.

The study objectives will be evaluated with analyses that include data from both Part A and Part B, if Part B is conducted. Analyses will also be performed separately for each study part. In general, the efficacy analyses will be analyzed with the ITT population and all other analyses will be performed with the As-treated population.

All statistical tests will be 2-sided at an alpha = 0.1 significance level unless stated otherwise. There will be no adjustment for multiplicity.

Data analyses will be performed using SAS[®] version 9.3 or higher (SAS Institute Inc., Cary, NC) in a UNIX environment.

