before at T = 0 and serial MRS scans and blood samples will be collected at T = 5 and 14 hours. On Day 36, following an overnight fast, a final MRS scan will be performed alongside a blood test at T = 24 hours.

A follow-up visit will be performed 28 days after the last dose of investigational product for safety assessments.

TARGET SUBJECT POPULATION

Subjects aged \geq 18 years, with body mass index \geq 27 and \leq 40 kg/m², a diagnosis of T2DM on metformin monotherapy, and a glycated haemoglobin of \leq 8.0% will be enrolled in the study. Females must not be pregnant and lactating females will be excluded. Females of childbearing potential should be using appropriate contraception.

TREATMENT GROUPS AND REGIMENS

Part A:

Following a screening period of up to 60 days, subjects will be randomised to receive either MEDI0382 or placebo once daily in the morning via SC injection as follows:

- MEDI0382 [REDACTED]
- Placebo for 28 days (N = 10)

Part B:

Following a screening period of up to 60 days, subjects will be randomised to receive either MEDI0382, placebo, or open-label liraglutide once daily in the morning via SC injection as follows:

- MEDI0382 [REDACTED]
- [REDACTED]
- Open label liraglutide 0.6 mg for 7 days, followed by 1.2 mg for 7 days, followed by 1.8 mg for 21 days (N = 10)

STATISTICAL METHODS

Sample size:

In Part A the sample size of 8 completers in each MEDI0382 and placebo groups provides \sim 80% power to detect a difference of 19% reduction in the baseline glycogen concentration adjusted for liver volume (as measured by MRS at T = 4 hours post standardised liquid morning meal) after 28 days of treatment in the MEDI0382 versus placebo arms. This is under the assumption of baseline glycogen content of 283 μ mol/mL and standard deviation of 41 μ mol/mL for both groups and a two-sided significance level at 0.1 (Krssak et al, 2004; Rothman et al, 1991).

In Part B the sample size of 10 completers in each MEDI0382 and placebo groups provides $>$ 80% power to detect a 24.2% reduction in fasting glycogen concentration adjusted for liver volume (as measured by MRS at T = 24 hours post standardised liquid morning meal) after 35 days of treatment in the MEDI0382 versus placebo arms. This is under the assumption of a common standard deviation of 17.0 % for both groups, a two-sided significance level at 0.05 and is based on the results of Part A.

Statistical analyses:

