3.4.1.3 Primary Efficacy Analysis

The primary efficacy analysis will be performed using the ITT population.

The primary endpoint, change in hepatic glycogen concentration (measured by MRS, adjusted for liver volume) at T = 4 hours post standardized morning meal from baseline (Day -1) to the end of 28 days of treatment will be analyzed using an analysis of covariance (ANCOVA) model with baseline covariate and treatment group. Pairwise comparisons between MEDI0382 and placebo will be performed within this analysis (Part A only).

The primary endpoint, percentage change in fasting hepatic glycogen concentration (adjusted for liver volume) as measured by MRS at T=24 hours post standardized morning meal from baseline (Day 1) to the end of 35 days of treatment (Day 36), will be compared between the MEDI0382 and placebo groups using an analysis of covariance (ANCOVA) model adjusting for baseline value and treatment group (Part B only).

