3.4.2.2 Secondary Efficacy Analyses

The secondary efficacy analyses will be performed using the ITT population.

The percentage change in fasting hepatic glycogen concentration (measured by MRS, adjusted for liver volume) at T = 24 hours post standardized morning meal from baseline (Day 1) to the end of 35 days of treatment, will be compared between MEDI0382 and liraglutide groups only in Part B of the study. This will be done using the ANCOVA model adjusting for baseline value and treatment group. A similar analysis will be applied to measure change in hepatic fat fraction from baseline (Day -1 or Day 1) to the end of 35 days of treatment (Day 35 or 36) versus placebo (Part B only).

The percentage change in fasting glycogen concentration (measured by MRS, adjusted for liver volume) at T = 24 hours post standardized morning meal from baseline (Day -1) to the end of 28 days of treatment, will be compared between MEDI0382 and placebo groups only in Part A of the study. This will be done using the ANCOVA model adjusting for baseline value and treatment group. A similar analysis will be applied to measure change in hepatic fat fraction from baseline (Day -1) to the end of 28 days of treatment versus placebo (Part A only).

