3.6 Safety Analyses

3.6.1 Adverse Events and Serious Adverse Events

Adverse events will be coded with MedDRA version 21.0 or higher. Analysis of adverse events will include the type, incidence, severity and relationship to study investigational product summarized by MedDRA System Organ Class (SOC) and Preferred Term (PT) by study part treatment group as well as for combined study parts. The AEs summaries will include only treatment-emergent AEs, ie, those occurring after initial administration of investigational product. Subjects will be counted once for specific PT or MedDRA SOC when calculating incidence rates. If the same AE Preferred Term occurs multiple times within a subject, the highest severity and level of relationship observed will be reported. Non-treatment-emergent AEs/serious adverse events (SAEs) will be presented in the listings.

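### As visibly written, SAP 3.1's two-sided 0.10 default governs the Part B primary test, which the protocol planned at two-sided 0.05

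*SAP*

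**What the plan says.** **Test level.** SAP 3.1 states: "All statistical tests will be 2-sided at an alpha = 0.1 significance level unless stated otherwise". It adds that multiplicity is not adjusted for. In SAP 3.4.1.3 the Part B primary test is an ANCOVA "model adjusting for baseline value and treatment group (Part B only"), with no significance level attached. SAP 3.4.2.2 gives none for the Part B comparisons with liraglutide or on hepatic fat fraction either.

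**Planning level.** The sample-size paragraphs of the protocol synopsis treat the parts differently. Part A is planned with a common SD "for both groups and a two-sided significance level at 0.1". Part B assumes "a two-sided significance level at 0.05 and is based on the results of Part A". Protocol 4.8.3.1 and 4.8.3.2 describe the ANCOVAs without a test level. Protocol 4.8.2 and SAP 2.4, both titled Sample Size, are redacted.

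**Analysis set.** SAP 3.1 also says: "The study objectives will be evaluated with analyses that include data from both Part A and Part B, if Part B is conducted". The next sentence adds separate analyses by part. Protocol 4.8.1 reverses the emphasis: separate evaluation, with combined cohorts where appropriate. SAP 3.4.2.2 confines the Part A fasting glycogen test, which "will be compared between MEDI0382 and placebo groups only in Part A of the study", and likewise the liraglutide test, which "will be compared between MEDI0382 and liraglutide groups only in Part B of the study". Adverse events are summarised by part "as well as for combined study parts" (SAP 3.6.1).

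**Sizing rule.** SAP 2.2 requires the combined sample of both parts to give at least 80% power and makes Part B conditional on needing no more than 10 per arm. SAP 1 cites protocol Amendment 6, and SAP 4 reports the Part A analysis in the past tense.

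**The concern.** The SAP default matches the protocol's planning level for Part A but not for Part B. Nothing visible in SAP 3.4.1.3 switches the Part B test to the stricter level. Read literally, the Part B primary comparison would be judged at twice the error rate used to size it. A p-value between 0.05 and 0.10 could then be reported as positive under the SAP and negative by the protocol's planning level.

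Two smaller points concern wording. SAP 3.1 is broader than the models SAP 3.4 specifies, because no pooled primary or secondary efficacy model is defined. SAP 2.2 describes Part B as still to be decided and sized jointly with Part A, whereas the protocol sizes it on its own.

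**Working it through.** **Inputs (protocol synopsis, sample size).**
- Part B: 10 completers per arm, difference 24.2, SD 17.0, two-sided 0.05, stated power above 80%. The 24.2% and 17.0% are read as percentage points on the percentage-change scale.
- Part A: 8 completers per arm, 19% of a baseline of 283, SD 41, two-sided 0.1, stated power about 80%.

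**Step 1. Reproduce the stated power.** Two-sample t-test, noncentrality = difference / (SD × √(2/n)), df = 2n − 2.
- Part A: difference 0.19 × 283 = 53.77; standard error 41 × √(2/8) = 20.5; noncentrality 2.62; df 14. Power is 80.2% at 0.10, which matches. At 0.05 it would be 68.4%, so the Part A figure depends on 0.10.
- Part B: standard error 17 × √(2/10) = 7.603; noncentrality 24.2 / 7.603 = 3.18; df 18. Power is 85.3% at 0.05 (85.1% with one df lost to the baseline covariate), consistent with the stated figure.

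**Step 2. Part B under the SAP default.** With the same inputs at two-sided 0.10, power is 92.1%.

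**Step 3. Smallest observed difference that reaches significance.** Critical t × 7.603.
- At 0.05: 2.101 × 7.603 = 15.97 points.
- At 0.10: 1.734 × 7.603 = 13.18 points.
- With 17 df for the ANCOVA: 16.04 and 13.23.

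**Step 4. How often the two levels disagree.** This is the difference between the two rejection probabilities.
- No true effect: 0.100 − 0.050 = 5% of trials.
- True difference 24.2: 0.921 − 0.853 = about 7% of trials.

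**Step 5. The SAP 2.2 rule at the planning values.** For 80% power the total per arm is 9 at 0.05 (power 80.9%) or 7 at 0.10 (80.6%), over both parts together. The protocol's 10 per arm in Part B reads instead as a stand-alone size, and Step 1 reproduces its power from Part B data alone.

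**The case against.** **The alpha mismatch may be resolved in redacted text.** The default carries an exception clause, and the redacted sample-size sections are where a 0.05 for Part B would most naturally be repeated. The protocol's 0.05 is also a planning assumption. A reader might infer that the protocol and SAP state contradictory test levels. They do not, because the protocol's analysis sections state none. This stands as a limit on certainty. It does not supply a level in SAP 3.4.1.3, where an analyst would look for one.

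**An exploratory Phase 2 study may use 0.10.** It may, and SAP 3.1 is open about not adjusting for multiplicity. The difficulty is that the protocol planned the two parts at different levels and the visible SAP carries only one.

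**Pooling is largely handled.** A reader might infer from SAP 3.1 that a pooled p-value decides the efficacy objectives. The documents do not support that. Separate analyses are planned in the next sentence, and SAP 3.4 ties each primary and secondary test to a single part. The two primary endpoints differ in scale, time point and treatment duration, so they cannot be pooled as defined. Combined data also have other uses: adverse events, and probably exploratory efficacy, since SAP 3.4.3.2 appears to allow combined analyses where SAP 3.5.1.2 allows only separate ones. Any inflated error rate for a decisive pooled test would therefore describe an analysis the SAP does not specify, and none is relied on here.

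**SAP 2.2 changes no analysis.** A reader might infer that Part B was wrongly sized. It was not: 10 per arm satisfies both the 80% floor and the ceiling of 10. The wording is only out of date.

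**Conclusion.** The alpha point holds on the visible text and should be corrected. As written, the Part B primary test defaults to two-sided 0.10 against a planning level of 0.05. That lowers the significance threshold from about 16.0 to 13.2 points and raises power at the planning values from 85% to 92%. The figures assume 10 completers per arm, an SD of 17 points as the residual SD, and a t-test approximation to the ANCOVA. The conclusion also assumes that no exception sits in the redacted sections, which keeps confidence at medium. None of the protocol's stated power figures is wrong. The pooling sentence in SAP 3.1 and the sizing rule in SAP 2.2 are drafting matters and add no weight to the point.

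**What to change.** **Main change.**
- SAP 3.4.1.3: add that the Part B primary comparison is tested at two-sided 0.05. The 0.10 default then agrees with the protocol's planning level for Part A.
- SAP 3.4.2.2: state the level for the Part B liraglutide and fat-fraction comparisons. The visible protocol gives none, so the sponsor must choose: 0.05 to match the primary test, or 0.10 said explicitly.
- If a redacted section already sets the Part B level, repeat it in SAP 3.4.

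**Tidying.**
- SAP 3.1: say that the primary and secondary efficacy objectives are evaluated by the part-specific analyses in SAP 3.4, and that any pooled MEDI0382-placebo analysis at T = 24 hours is supportive and includes a study-part term.
- SAP 2.2: replace the combined-sample and conditional wording with the protocol's stand-alone basis for Part B (10 completers per arm, 24.2%, SD 17.0%, two-sided 0.05).

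**Cost.** SAP wording only. Testing Part B at 0.05 instead of 0.10 lowers power at the planning values from 92% to 85%, still above the stated 80%. A pooled estimate can still be reported as supportive.
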